### **14.2. Sample Size Justification**

Sample size for Phase 1 was not determined on the basis of statistical considerations because it is primarily for the collecting clinical data to calculate the required sample size for Phase 2.

Sample size requirements for Phase 2 were based on assumptions derived from the analysis of selected data collected in Phase 1. It was calculated that the total sample size of 120 subjects to complete (40 per group) the study provides at least 90% power to test each primary and secondary hypothesis. The sample size and power calculations were performed using a paired sample *t*-test approach (exact method) in PASS (NCSS, 2021).

A gate-keeping approach will be used to control the study-wise Type I error rate at the one-sided 0.025 level and adjust for multiplicity due to multiple efficacy endpoints of interest in combination of Bonferroni adjustment. The null hypothesis for the primary efficacy endpoints has to be rejected at one-sided alpha level of 0.025 first, in order to propagate the full alpha to the secondary family of hypothesis tests. The Bonferroni approach will apply then to testing the secondary efficacy endpoints.

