# Clinical Study Protocol

## Johnson & Johnson Vision

The sample size estimates for primary endpoints were calculated using 1-sided Type I error rate of 0.025 for each endpoint. The sample size estimates for the two secondary endpoints were adjusted using a Bonferroni adjustment and calculated using a one-sided Type I error rate of 0.0125 (i.e., one-sided 0.025/2).

While no Toric wearers were enrolled in Phase 1, it is anticipated that the multifocal group would require the largest sample due to simultaneous optics of the multifocal lens and the intraocular scattering that naturally occurs with age, which can both compromise and reduce the quality of vision. Hence it is expected that the sample size required to test endpoints for Toric wearers would be no more than the sample size required for Multifocal wearers. As these endpoints did not have data from Phase 1, all hypotheses for the Toric wearers will be exploratory endpoints.

Table 9 displays the statistical power and associated sample sizes estimates derived for the primary and secondary endpoints for Sphere and Multifocal groups, given the assumed treatment effect sizes. Based on the table below, it is planned that Phase 2 will enroll approximately 135 subjects (45 subjects per group) with the target of 120 subjects (40 subjects per group) to complete the study, assuming approximately a 10% drop-out rate.

Table 9: Assumptions for Power and Sample Size Calculations for The Primary and Secondary Endpoints

Endpoint Type	Endpoint (Subject Group)	Standard Deviation of Paired Differences	Effect Size	Alpha	Power	Sample Size Per Group
Primary	Visual Range (Sphere)	0.10	1.83	0.05	0.94	6
	Visual Range (Multifocal)	0.23	0.52	0.05	0.90	41
Secondary	Motion Detection (Sphere)	1.16	0.99	0.03	0.92	16
	Brightness Perception (Multifocal)	0.20	0.70	0.03	0.91	29

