# Clinical Study Protocol

## Johnson & Johnson Vision

### 14.4. Level of Statistical Significance

Although the Test and Control lenses are senofilcon A based lenses with and without the new UV/HEV filter, respectively, the study lenses assigned to each subject group will be different with different optical designs specifically for vision correction of the sphere, multifocal, and toric (astigmatism) lens wearers. Therefore, the planned hypotheses in Phase 2 will be tested separately for each subject group without Type I error adjustment across the three subject groups, due to different optical designs of the study lenses for different groups. The primary hypothesis for each subject group will be tested using a one-sided Type I error rate of 0.025. The secondary hypotheses will be tested only when the primary hypothesis is met for the same subject group. For secondary hypotheses, the Type I error rate will be adjusted using the Bonferroni approach for the two secondary hypotheses and each secondary hypothesis will be tested using the Bonferroni adjusted one-sided Type I error rate 0.0125 (i.e., one-sided 0.025/2).

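### Section 14.2's power for the multifocal brightness secondary leaves out the gate: the chance of reaching that claim at 40 completers is about 0.87 to 0.89, not at least 0.90

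*Combined protocol and SAP*

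**What the plan says.** Section 14.2 plans 120 completers, 40 in each of three groups, and states that "the study provides at least 90% power to test each primary and secondary hypothesis". The method is given in the same paragraph: "The sample size and power calculations were performed using a paired sample *t*-test approach (exact method) in PASS".

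The next paragraph of Section 14.2 sets up the gate: "The null hypothesis for the primary efficacy endpoints has to be rejected at one-sided alpha level of 0.025 first". Section 14.4 narrows it to the group: "The secondary hypotheses will be tested only when the primary hypothesis is met for the same subject group".

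On the error rates behind the calculations, Section 14.2 says "The sample size estimates for primary endpoints were calculated using 1-sided Type I error rate of 0.025 for each endpoint", and that the two secondaries were run at one-sided 0.0125 after a Bonferroni split. That split is the only adjustment described for the secondaries. Table 9 then gives, for multifocal wearers:

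- visual range (primary): effect size 0.52, power 0.90, 41 subjects;
- brightness perception (secondary): effect size 0.70, power 0.91, 29 subjects.

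Neither the text nor the table gives the probability of passing the gate and then the secondary, and no correlation between the endpoints is stated.

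**The concern.** A gated secondary can be declared only when two tests succeed. The probability of that is a joint probability, and it cannot exceed the power of the weaker test at the same sample size. In the multifocal group the weaker test is the gate itself: visual range has effect size 0.52, against 0.70 for brightness. A power quoted for brightness as though its test were always performed therefore overstates the chance of the claim.

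Brightness in multifocal wearers is a formal secondary hypothesis (Section 2, Secondary Hypotheses - Phase 2), and Section 2.1 says that the results may support marketing claims. A reader of Section 14.2 would take the chance of reaching the brightness claim to be 90% or better.

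**Working it through.** **Inputs.** Effect sizes, sample sizes and powers are from Table 9. The one-sided alphas are 0.025 (primary) and 0.0125 (secondary), from the text of Section 14.2; Table 9 prints the two-sided equivalents, 0.05 and a rounded 0.03. The planned size is 40 completers per group. The correlation between the two multifocal paired differences is not in the documents, so the full range is shown.

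**Formula.** Exact one-sided paired t-test power is 1 − F(t_crit; n − 1, d√n). Here F is the noncentral t distribution function with n − 1 degrees of freedom and noncentrality d√n, and t_crit is the upper-alpha point of the central t.

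**Step 1: reproduce Table 9.**

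| Row | n | d√n | t_crit | Power | Table 9 |
|---|---|---|---|---|---|
| Visual range, sphere | 6 | 1.83 × √6 = 4.483 | 2.571 | 0.943 | 0.94 |
| Visual range, multifocal | 41 | 0.52 × √41 = 3.330 | 2.021 | 0.901 | 0.90 |
| Motion detection, sphere | 16 | 0.99 × √16 = 3.960 | 2.490 | 0.916 | 0.92 |
| Brightness, multifocal | 29 | 0.70 × √29 = 3.770 | 2.369 | 0.912 | 0.91 |

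All four rows reproduce with no gate term, so the secondary powers are marginal.

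**Step 2: the multifocal tests at the planned 40.**

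- Visual range: 0.52 × √40 = 3.289, t_crit 2.023, power 0.8938.
- Brightness alone: 0.70 × √40 = 4.427, t_crit 2.331, power 0.9793.

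**Step 3: apply the gate at 40.**

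- Independent endpoints: 0.8938 × 0.9793 = 0.875.
- Lowest possible under any dependence: 0.8938 + 0.9793 − 1 = 0.873.
- Highest possible: the smaller of the two, 0.894.
- Simulated joint power under bivariate normality: about 0.883 at correlation 0.5 and 0.893 at correlation 0.9.

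**Step 4: rounding of the effect sizes.** The printed 0.52 could be anything from 0.515 to 0.525, which puts visual range power at 40 between 0.888 and 0.899. The ceiling on gated brightness moves with it and stays just below 0.90. With both effect sizes at the bottom of their rounding ranges (0.515 and 0.695), the floor is 0.8880 + 0.9778 − 1 = 0.866.

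**Step 5: separate the two causes.** The distance from 0.90 to 0.894 is the primary's own shortfall, because Table 9 needs 41 and the plan has 40. The gate's further cost is at most 0.8938 − 0.8731 = 0.021. If the primary were put right at 41, visual range would have 0.9013 and brightness alone 0.9820, and gated brightness would be 0.9013 × 0.9820 = 0.885 under independence (0.883 to 0.901 under any dependence).

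**Step 6: sphere motion detection at 40.** Visual range in sphere wearers has power 1.000 to three decimals and motion detection has 0.9999, so the joint probability under Section 14.4's own-group gate is above 0.999. The gate costs nothing there.

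**The case against.** The strongest reply is that Section 14.2 speaks of power per hypothesis, names the paired t-test and gives the alpha for each secondary. Read as marginal power, the statement is true for brightness at 40 completers (0.979). Table 9 contains no miscalculation on this point, and the documents nowhere promise a joint power. That stands as far as it goes: this is an omission in what the figure represents, not an error of arithmetic. It does not dispose of the point, because the paragraph that follows makes the test conditional. A marginal power then describes a test that the plan will not always carry out, and nothing in the text marks it as marginal.

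The practical weight is also modest. The effect sizes come from Phase 1, which aimed for about 10 multifocal completers. If 0.52 were the estimate from 10 subjects (an assumption), its exact 95% interval would run from about −0.16 to 1.17, which dwarfs a correction of 1 to 3 points. Section 14.8 asks only for at least 80% power on the primary. Enrolment is approximate, and Sections 4.3 and 8.2 provide for replacing subjects who discontinue.

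Three stronger readings are tempting and should be resisted.

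- A reader might conclude from Table 9's 29 that the brightness claim has at most about 77% power, which is visual range's power at 29. But 29 is not the planned size, and the same group's primary row shows 41.
- A reader might infer that sphere motion detection drops to 0.894, by taking Section 14.2's gate to require both primaries. Section 14.4 ties the gate to the same subject group, and any tension between the two sections is a separate matter.
- A reader might say that 43 completers are needed. That is the figure under independence (0.9148 × 0.9864 = 0.902). At 42 the joint power is 0.894 under independence but about 0.900 at correlation 0.5, and the documents give no correlation.

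**Conclusion.** The point holds in a limited form, and its severity is minor. At the planned 40 completers the probability of being allowed to test multifocal brightness and then succeeding is about 0.875 under independence. It lies between 0.873 and 0.894 whatever the dependence, with a ceiling of 0.899 after allowing for rounding of 0.52. The 90% statement therefore does not hold for that claim under the plan's own testing rule, although the marginal power of the brightness test is well above 90%.

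The shortfall is 1 to 3 points and confined to one group. It comes partly from the primary having 40 completers against Table 9's 41. Moving to 41 would not by itself settle it: gated brightness would still be about 0.885 under independence. The result rests on Table 9's effect sizes being the true ones, the stated one-sided alphas, 40 evaluable completers, and the own-group gate of Section 14.4.

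**What to change.** In Section 14.2:

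- Remove the 90% statement for multifocal brightness and give its gated power as about 0.87 to 0.89 at 40 completers. State that the range reflects the unknown correlation between visual range and brightness.
- Keep the statement for sphere motion detection, noting that it exceeds 0.999 after the own-group gate.
- Label the secondary powers and sizes in Table 9 (16 and 29) as marginal, before the gate.

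This costs a sentence and a table footnote. It changes no sample size, test, alpha or study procedure; the only consequence is a slightly less favourable figure for brightness.

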##### Visual Range

The visual range metric will be analyzed separately for two of the three subject groups (i.e., Spherical wearers and Multifocal wearers) using a linear mixed model. The analysis will be conducted on the ITT population. An appropriate distribution from the exponential family (e.g., normal or lognormal) will be considered for the linear mixed modeling based on the distribution of the endpoint. The model will include lens type, lens sequence, and period as fixed effects. Other baseline and subject characteristics such as age, gender, race, and iris color will be included as fixed covariates when appropriate. An unstructured (UN) covariance matrix will be used to model the residual errors among within-subject repeated measures (R-side). If the model fails to converge, a Compound Symmetric (CS) matrix may be considered. The Kenward and Roger method will be used for the denominator degree of freedom.

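### Section 14.2 claims study-wise Type I error control at one-sided 0.025, but Sections 14.4 and 14.5 test two primary hypotheses at 0.025 each without adjustment, a nominal rate of about 4.9%

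*Combined protocol and SAP*

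**What the plan says.** Section 14.2 (Sample Size Justification) makes the overall claim: "A gate-keeping approach will be used to control the study-wise Type I error rate at the one-sided 0.025 level". It then describes the gate: "The null hypothesis for the primary efficacy endpoints has to be rejected at one-sided alpha level of 0.025 first", after which the full alpha passes to the secondary family and Bonferroni is applied there. The same section sizes the primaries without a split: "The sample size estimates for primary endpoints were calculated using 1-sided Type I error rate of 0.025 for each endpoint".

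Section 14.4 (Level of Statistical Significance) says that the Phase 2 hypotheses "will be tested separately for each subject group without Type I error adjustment across the three subject groups", giving the different optical designs as the reason. It continues: "The primary hypothesis for each subject group will be tested using a one-sided Type I error rate of 0.025". Its gate is: "The secondary hypotheses will be tested only when the primary hypothesis is met for the same subject group". For the secondaries, "the Type I error rate will be adjusted using the Bonferroni approach for the two secondary hypotheses", which gives one-sided 0.0125 each.

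Section 14.5 adds: "The visual range metric will be analyzed separately for two of the three subject groups", namely sphere and multifocal. Superiority is declared on each group's own confidence limit.

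The Hypotheses section lists two primaries (visual range in sphere wearers and in multifocal wearers) and two secondaries (motion detection in sphere wearers, brightness perception in multifocal wearers). Toric hypotheses are exploratory.

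**The concern.** A study-wise rate of 0.025 means that the chance of any false confirmatory claim in the study is at most 2.5%. Two primaries, each tested at the full 0.025 and each able to succeed alone, cannot have that property unless something links them: a split of alpha, a fixed order, or a rule that both must be met. The plan states none of these.

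Two further inconsistencies follow.

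- Each group has exactly one secondary, so dividing 0.025 by two is itself an adjustment across groups. That sits badly with the statement in 14.4 that there is none.
- The gate in 14.2 refers to the primary endpoints in the plural and can be read as needing both. The gate in 14.4 needs only the same group's primary.

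Section 2.1 says the results may be used to support marketing claims. A report that repeats 14.2 would state an error rate the procedure does not have. If only one primary succeeded, whether that group's secondary may be tested could be argued with the data in hand.

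**Working it through.** **Inputs.** One-sided 0.025 per primary and 0.0125 per secondary (14.2, 14.4). Effect sizes from Table 9: visual range 1.83 (sphere) and 0.52 (multifocal); motion detection 0.99 (sphere); brightness 0.70 (multifocal). Target of 40 completers per group (14.2).

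**Step 1: which alpha Table 9 used.** Exact one-sided paired-t power is P(T > t₁₋α) with n − 1 degrees of freedom and noncentrality (effect size × √n).

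| Endpoint | n | Noncentrality | One-sided α | Power | Table 9 |
|---|---|---|---|---|---|
| Visual range, sphere | 6 | 1.83√6 = 4.48 | 0.025 | 0.943 | 0.94 |
| Visual range, multifocal | 41 | 0.52√41 = 3.33 | 0.025 | 0.901 | 0.90 |
| Motion, sphere | 16 | 0.99√16 = 3.96 | 0.0125 | 0.916 | 0.92 |
| Brightness, multifocal | 29 | 0.70√29 = 3.77 | 0.0125 | 0.912 | 0.91 |

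At 0.0125 the two primary rows would give 0.854 and 0.837, which do not match. The primaries were therefore sized with no split across groups. (The alphas printed in Table 9, 0.05 and 0.03, agree with the text only as two-sided values, with 0.025 rounded to 0.03.)

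**Step 2: error rate under the 14.4 rules.** The groups are disjoint and modelled separately, so the tests are taken as independent and of exact size. A group's secondary is reached only through that group's primary.

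- Both primary nulls true: 1 − 0.975² = 0.0494.
- One primary effective with its gate passed almost surely, all other nulls true: 1 − 0.975 × 0.9875 = 0.0372.
- Both primaries effective with both gates passed, both secondary nulls true: 1 − 0.9875² = 0.0248.

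Only the last case is within 0.025. Without independence, the Bonferroni bound for the two primaries is 0.05.

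**Step 3: how often the two gate readings would differ.** They differ when exactly one primary succeeds. At n = 40 and one-sided 0.025, power is 1.000 for sphere and 0.8938 for multifocal (noncentrality 0.52√40 = 3.29). The probability is 1.000 × (1 − 0.8938) = 0.106.

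**Step 4: price of real study-wise control.** With each primary at 0.0125, the same-group gate, and each secondary at 0.0125:

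- Nominal rate: 1 − 0.9875² = 0.0248.
- Multifocal visual-range power at n = 40: 0.8265, down from 0.8938. Reaching 0.90 takes 49 completers, or 55 enrolled at 10% drop-out (49/0.9 = 54.4, rounded up).
- Brightness power at n = 40 is 0.9793 before its gate. With the gate, and the two endpoints assumed independent, it goes from 0.8938 × 0.9793 = 0.875 to 0.8265 × 0.9793 = 0.809.
- Sphere visual-range power stays at 1.000.

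**The case against.** The strongest reply is that nothing is hidden. Section 14.4 says openly that there is no adjustment across groups and gives a reason: the lenses differ in optical design, so each group answers its own question. The study is labelled Feasibility, and an analyst following 14.4 and 14.5 has a usable rule. All of that stands. A reader might infer that the missing adjustment is itself an error, or that the sample size is wrong. The documents support neither: testing by group is a reasonable choice, and Table 9 is consistent with it. Disclosure in 14.4 does not, however, make the study-wise statement in 14.2 true, and 14.2 nowhere says that study-wise means within a group.

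A reader might also infer that 14.2 definitely requires both primaries before any secondary. It does not say so: the word for the null hypothesis is singular and no term for both appears. That is one reading, and 14.4 is the more explicit text, so the 0.106 measures an ambiguity and not a certain conflict.

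Finally, it is tempting to ask 14.4 to justify 0.0125, or to call it a deliberately conservative choice. Section 14.4 already gives the reason, Bonferroni over the two secondaries. What it lacks is the recognition that those two lie in different groups.

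**Conclusion.** The point holds as a contradiction between sections in force, and it is minor. Section 14.2 states an error property that the rules in 14.4 and 14.5 do not have. The nominal rate across the two primaries is about 4.9% against the stated 2.5%, assuming independent groups and tests of exact size. The internal mix in 14.4 and the ambiguous gate are matters of clarity that the same edit resolves.

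The 4.9% should not be read as a verdict on every part of the analysis. The rule in 14.5 that restricts the analysis to period 1 after a significant sequence effect raises its own question about test size. It is separate and forms no part of this point. The toric tests are exploratory and are not counted.

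**What to change.** Before unmasking, replace the study-wise and gate sentences in 14.2 with text such as:

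*Each group's visual-range primary is tested at one-sided 0.025 with no adjustment across groups for the primary hypotheses, so the nominal rate across the two primaries is about 0.049. Each group's secondary is tested only if that group's primary null is rejected, at one-sided 0.0125 (Bonferroni across the two secondaries, one in each group).*

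In 14.4, limit the no-adjustment statement to the primary hypotheses, so that it no longer contradicts the Bonferroni split of the secondaries.

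This changes wording only. Tests, alpha levels, decision rule and sample size stay as they are. The cost is a less favourable stated error rate.

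If the sponsor wants study-wise 0.025 to be true, one route is to test each primary at 0.0125, keep the same-group gate and keep each secondary at 0.0125, changing 14.2, 14.4 and 14.5 to match. At 40 completers that costs multifocal visual-range power (0.894 to 0.827) and gated brightness power (0.875 to 0.809), or else requires 49 multifocal completers to restore 0.90 for visual range.

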### **Primary Hypotheses - Phase 2**

The statistical hypotheses to meet the primary study objective of Phase 2 will be defined on the basis of the Phase 1 clinical results to make the adequate efficacy assumptions to power the Phase 2 of the study appropriately.

1. Subjects wearing the Test lens will have statistically significantly improved visual range than the Control lens among spherical wearers.
2. Subjects wearing the Test lens will have statistically significantly improved visual range than the Control lens among multifocal wearers.

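### Sections 14.2 and 14.4 give inconsistent gates to the secondary tests, so the status of sphere motion detection is unsettled if multifocal visual range is missed

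*Combined protocol and SAP*

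**What the plan says.** Section 2 names two primary hypotheses for Phase 2, one per group. The sphere one reads "Subjects wearing the Test lens will have statistically significantly improved visual range than the Control lens among spherical wearers", and there is a parallel one for multifocal wearers. There are also two secondary hypotheses, one per group: motion detection for sphere wearers and brightness perception for multifocal wearers.

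Section 14.2 describes the testing strategy at study level. "A gate-keeping approach will be used to control the study-wise Type I error rate at the one-sided 0.025 level", combined with a Bonferroni adjustment. "The null hypothesis for the primary efficacy endpoints has to be rejected at one-sided alpha level of 0.025 first", and the purpose given is "in order to propagate the full alpha to the secondary family of hypothesis tests". Bonferroni is then applied to the secondary endpoints.

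Section 14.4 describes it at group level. Hypotheses are tested separately by group "without Type I error adjustment across the three subject groups". On the primaries it states: "The primary hypothesis for each subject group will be tested using a one-sided Type I error rate of 0.025". Its rule for moving on from a primary is this: "The secondary hypotheses will be tested only when the primary hypothesis is met for the same subject group". For the secondaries, "each secondary hypothesis will be tested using the Bonferroni adjusted one-sided Type I error rate 0.0125", which is 0.025 divided by two.

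Sections 14.5 and 14.6 give the models and hypotheses but do not restate the gate. Section 14.8, on the interim analysis, does not settle it either.

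**The concern.** The two sections appear to answer one question differently: what must be rejected before a secondary hypothesis may be tested? Section 14.2 speaks of the primary endpoints together, of one secondary family, and of an error rate for the study. Section 14.4 speaks of the primary in the same group and makes no adjustment between groups. Both are current body text, and both describe the confirmatory decision.

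At stake is the standing of a secondary claim. Section 2.1 allows the results to be used for marketing claims. Multifocal visual range is the weaker of the two primaries, so the likely mixed outcome is sphere met and multifocal missed. The plan would then hold one rule that lets motion detection be claimed and another that stops it, and the choice between them could be made with the results in view.

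**Working it through.** **1. The two rules side by side.** Section 14.2 is read here as requiring the primary family to be rejected. VR is visual range.

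| Sphere VR | Multifocal VR | Secondaries open under 14.2 | Secondaries open under 14.4 |
|---|---|---|---|
| met | met | motion and brightness | motion and brightness |
| met | missed | none | motion |
| missed | met | none | brightness |
| missed | missed | none | none |

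The rules differ in the two mixed rows.

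**2. Inputs.** From Table 9: effect sizes 1.83 (VR, sphere), 0.52 (VR, multifocal), 0.99 (motion, sphere) and 0.70 (brightness, multifocal). From 14.2: 40 completers per group and a paired t-test. From 14.4: one-sided alpha of 0.025 for each primary and 0.0125 for each secondary.

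**3. Reproducing Table 9.** Power = P(T > t), where t is the one-sided critical value on n − 1 degrees of freedom and T is noncentral t with noncentrality d√n.

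| Endpoint | n | One-sided alpha | Table 9 power | Recomputed |
|---|---|---|---|---|
| VR, sphere | 6 | 0.025 | 0.94 | 0.9425 |
| VR, multifocal | 41 | 0.025 | 0.90 | 0.9013 |
| Motion, sphere | 16 | 0.0125 | 0.92 | 0.9156 |
| Brightness, multifocal | 29 | 0.0125 | 0.91 | 0.9124 |

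All four reproduce. The alphas printed in Table 9 (0.05 and 0.03) are the two-sided equivalents, with 0.025 rounded to 0.03.

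**4. How often the rules diverge, at n = 40.**
- VR, sphere: noncentrality 1.83 × √40 = 11.57; power 1.000 to three decimals.
- VR, multifocal: noncentrality 0.52 × √40 = 3.29; power 0.894.
- The groups contain different subjects, so their results are independent. P(sphere met, multifocal missed) = 1.000 × (1 − 0.894) = 0.106.
- The reverse mixed outcome has negligible probability because sphere power is essentially 1.

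The plan gives only 0.52 for the multifocal effect. Two smaller values, assumed here, show the sensitivity:

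| Multifocal effect (SD) | Multifocal VR power | P(rules diverge) |
|---|---|---|
| 0.52 (Table 9) | 0.894 | 0.106 |
| 0.45 (assumed) | 0.793 | 0.207 |
| 0.40 (assumed) | 0.694 | 0.306 |

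**5. Power for the sphere motion claim.** At n = 40 and one-sided 0.0125 the motion test alone has power 0.9999.
- Under 14.4: 1.000 × 0.9999 = 0.9999.
- Under 14.2: 1.000 × 0.8938 × 0.9999 = 0.894.

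**6. What each gate does to the error rate.**
- Sphere VR effect real (taken as certain to be rejected), other three nulls true. Under 14.4 a false claim arises if motion or multifocal VR is rejected: 1 − 0.9875 × 0.975 = 0.0372. Brightness adds nothing, since it opens only after multifocal VR has already been falsely rejected. Under 14.2 motion also opens only after that false rejection, so the rate is 0.025.
- Both primary effects real and certain to be rejected, both secondary nulls true: 1 − 0.9875² = 0.0248 under either gate.
- All four nulls true, either primary claimable alone: 1 − 0.975² = 0.0494 under either gate.
- Within one group, the primary at 0.025 followed by one gated secondary keeps the rate at or below 0.025, even if the secondary were tested at the full 0.025. The 0.0125 split therefore has no within-group purpose; it fits the cross-group family of 14.2.

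**The case against.** The best defence is that 14.2 is loosely worded and does not contradict 14.4. It uses a singular null hypothesis with plural endpoints, never says that both must be rejected, and gives no rule for the case where exactly one primary is met. It can be read distributively: each primary opens its own secondary, and 14.4, the section on significance levels, supplies the detail. On that view the specific rule governs.

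Part of this stands. A reader might infer that 14.2 expressly forbids the motion test after a multifocal miss. It does not say so; the bar follows from its natural reading. That reading is still the stronger one, because passing the full alpha to a single secondary family under study-wise control, with each primary tested at 0.025, fits only if the whole primary family is rejected. Nothing in 14.2 limits the gate to the same group, and no clause gives 14.4 precedence. Nor does 14.4 stand alone, since it keeps a Bonferroni split across two secondaries that lie in different groups.

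A reader might also infer that 14.4 is plainly the intended rule and that one replacement sentence in 14.2 is enough. The documents do not support this either. The change history for version 5.0 lists 14.2 among the updated sections and does not list 14.4, so it gives no ground for treating 14.4 as the later intention. And adopting the 14.4 gate alone would leave the neighbouring study-wise 0.025 statement untrue.

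On size, the synopsis labels the trial a feasibility study, and the 21% and 31% figures rest on assumed effects. Both are fair limits on the weight of the point.

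**Conclusion.** The point holds as an inconsistency to be reconciled between two operative sections. It is not a case of two explicit and opposite commands. Under the plan's own assumptions (Table 9 effects, 40 completers per group, independent groups) the sections lead to different decisions on sphere motion detection in about 11% of trials, and more often if the multifocal effect is smaller than assumed. Motion power is 0.9999 under one gate and about 0.89 under the other.

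The disagreement extends to the scope of error control. The group-level gate does not deliver study-wise 0.025: the chance of any false claim is 0.037 when only the sphere primary effect is real. The 0.049 for the two primaries under the global null arises with either gate if each primary may be claimed alone.

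A reader might infer that the primary conclusions are in doubt. They are not affected by this point: both sections test each primary at one-sided 0.025, and the gate governs only what follows. The change should be made, because a confirmatory rule ought to have one reading before results are known.

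**What to change.** Before database lock and unmasking, state one gate and one error-control scope, in the same terms, in 14.2 and 14.4. The choice is the sponsor's.

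**If the group-level gate of 14.4 is kept:**
- Replace the gate sentence in 14.2 with: *Within each subject group the secondary hypothesis is tested only if that group's visual-range hypothesis is rejected; failure in one group does not close testing in the other.*
- Change the study-wise 0.025 claim in 14.2 to control within each subject group.
- State in both sections whether 0.0125 for each secondary is retained as a conservative choice or is not needed, given one secondary per group.

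**If the study-level gate of 14.2 is kept:**
- Amend 14.4 to say that both primaries must be rejected before either secondary is tested at 0.0125.
- Remove "without Type I error adjustment across the three subject groups" and the same-group condition from 14.4.
- Say whether one primary may be claimed without the other; if it may, study-wise 0.025 still does not hold (0.049 under the global null).
- Note that motion power falls to about 0.89, just under the 90% that 14.2 states for every primary and secondary hypothesis.

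The cost is a few sentences in two sections. Visits, measurements, randomization and sample size are unchanged.
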